8.1.4 Sensitivity Analysis of Overall Survival

A sensitivity analysis of OS will be conducted in which subjects who are crossed over to Vigil therapy will be censored at the time of crossover.

8.1.5 Subgroup Analyses of the Primary (PFS) and Key Secondary Endpoints (OS, ORR)

Subgroup analyses will be conducted in the following subsets of the ITT population:

- Race / ethnicity
- Study site / region

- Age group (<15 years (low), ≥15 years (high))
- Gender
- Number of doses received (≤median number of doses administered, >median number of doses administered)
- Number of lines of prior treatments including chemotherapy and radiation
- At time of diagnosis: localized vs. metastatic disease
- At time of diagnosis: skeletal vs. extraskeletal
- At time of diagnosis: tumor volume/burden (<100ml or 8cm vs >100ml or 8cm)
- Response to frontline therapy (CR vs. PR vs. SD vs. progressive disease)
- Time to first recurrence: <2 years, > 2 years

8.2 Safety Analyses

Safety endpoints include all adverse events (CTCAE version 5.0), laboratory safety assessments, and physical examination findings.

8.3 Interim Analysis

An interim analysis for efficacy, futility, and potential sample size re-estimation will be conducted by an independent data monitoring committee (IDMC) when 40 PFS events have been achieved (60% information fraction). Based on the Lan-DeMets method for group sequential trials using O'Brien-Fleming boundaries (Reboussin, DeMets et al. 2000), the levels of significance for the interim and final analyses are alpha=0.00762 and alpha=0.0476, respectively.

Based on the results of the interim analysis, the IDMC will make one of the following four recommendations to the sponsor:

- Terminate the study for efficacy (p<0.00762 at the interim analysis);
- Continue the study as planned;
- Increase the sample size to 120 events;
- Terminate the study for futility.

Provided that the IDMC does not recommend terminating the study early for efficacy, the conditional power of the planned final analysis at 67 events will be computed using the methodology of (Harrington 2001) (Jennison and Turnbull 2000), under the assumption that the observed hazard ratio at the interim analysis represents the true effect. In terms of the HR observed at the interim analysis, these rules can be translated (approximately) as follows:

- If the HR is less than 0.43, terminate for efficacy
- If the HR is in the range from 0.43 to 0.51, continue as planned.
- If the HR is in the range from 0.51 to 0.61 (i.e., conditional power in the range from 50% to 80%), increase the sample size to 120 events.
- If the HR is greater than 0.61 (i.e., conditional power less than 50%), terminate for futility.

9.0 CONSIDERATIONS FOR DATA ANALYSIS

9.1 Programming Environment

All analyses will be conducted using SAS[®] version 9.0.

9.2 Statistical Notation and Methodology

Unless stated otherwise, the term "descriptive statistics" refers to the number of subjects (n), mean, median, standard deviation (STD), minimum (min), and maximum (max) for continuous data and frequencies and percentages for categorical data. Min and max values will be rounded to the precision of the original value, means and medians will be rounded to 1 decimal place greater than the precision of the original value, and STDs will be rounded to 2 decimal places greater than the precision of the original value. Percentages will be rounded to the nearest whole number (zeros are not displayed) with values of "< 1%" and "> 99%" shown as necessary for values falling near the boundaries. P-values will be presented with 3 decimal places and values less than 0.001 will be presented as < 0.001.

Unless otherwise noted, all data collected during the study will be included in data listings and will be sorted by cohort, subject number and then by date/time for each subject number.

10.0 DATA HANDLING METHODS

10.1 Missing Data

10.1.1 Date Values

In cases of incomplete dates (e.g., pertaining to AE, concomitant medication, medical history, etc.), the missing component(s) will be assumed as the most conservative value(s) possible. For example, if the start date has a missing day value, the first day of the month will be imputed for study day computations (i.e., treatment-emergent status, etc.). If day is missing for an end date, the last day of the month will be imputed. Similar logic will be assumed for missing month and year components.

Date imputation will only be used for computational purposes e.g., treatment-emergent status, etc. Actual data values as they appear in the original CRFs will be shown in the data listings.

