14.4 Recording of an Adverse Event

Adverse events will be recorded for the duration of a subject's time on study: following procurement of the subject's tissue for tissue manufacture and for up to 30 days following the last administration of Vigil. All AEs, regardless of causal relationship are to be recorded in the eCRF and source documentation. Additional information about each event, such as treatment

required, eventual outcome, and whether or not therapy had to be interrupted or dosages reduced, will also be recorded on the eCRF.

Pre-existing conditions will be recorded at baseline on the Medical History Form. If a preexisting condition does not change, it does not have to be reported as an AE on subsequent cycles.

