10.3 Data Derivations and Definitions

The following definitions and derivations will be used for this study:

Baseline for all assessments will be considered as the last non-missing assessment prior to the first administration of clinical trial material (CTM).

Change from baseline will be calculated as:

Change = observed value – baseline value.

Study days on or after the initial dose of CTM will be computed as:

Study Day = Date – Study Drug Start Date + 1.

For pre-dosing dates, Study Day = Date – Study Drug Start Date.

Age will be calculated from the date of birth to informed consent date.

Treatment-emergent events will be considered as any event occurring after the first dose of treatment drug and prior to a subject's termination, withdrawal or completion of the study.

Prior medications will be those ended before the first study treatment.

Concomitant medications are those used on or after the date of first study treatment.

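### The partial-date rule in SAP 10.1.1 classes every adverse event with a missing onset day in the month of first dose as pre-treatment, so it drops out of the treatment-emergent summaries

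*SAP*

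**What the plan says.** SAP 10.1.1 covers incomplete dates for AEs, concomitant medications and medical history together. Its principle is that "the missing component(s) will be assumed as the most conservative value(s) possible". Its example is that "if the start date has a missing day value, the first day of the month will be imputed for study day computations", and the same sentence gives treatment-emergent status as the purpose. A missing end day goes to the last day of the month. For larger gaps, "Similar logic will be assumed for missing month and year components". The section then limits the scope: "Date imputation will only be used for computational purposes e.g., treatment-emergent status, etc". The listings keep the dates as recorded.

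SAP 10.3 defines a treatment-emergent event as "any event occurring after the first dose of treatment drug", up to the end of the subject's participation. It gives dates before the study drug start a negative study day. SAP 13.2 adds a second, descriptive definition: an event that emerges during treatment or worsens compared with before. It contains no rule for partial dates.

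Protocol 14.4 starts AE recording after procurement of the subject's "tissue for tissue manufacture and for up to 30 days following the last administration of Vigil". Pre-dose and post-dose events therefore sit in one database, and the onset date has to separate them.

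**The concern.** For a safety analysis, the conservative treatment of an event of uncertain timing is to keep it among the treatment-emergent events. The SAP's example does the reverse. The first of the month can never fall after a first dose given in that same month, so an AE known only to have begun in that month is always placed on or before first dose.

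The rule does no harm to concomitant medications. SAP 10.3 classes a medication as prior by when it ended, and a missing end day goes to the last of the month. The convention appears to have been carried over to AE onset, where it works the wrong way.

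At stake are seven of the eight AE summaries in SAP 13.2: all treatment-emergent events, those leading to discontinuation, by relation, by severity, serious, serious by relation, and fatal. The direction of error is always an undercount, and it falls on the earliest events, when chemotherapy begins.

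**Working it through.** The plan states no figure on this point, so there is none to reproduce. The check applies the rule literally.

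**One case.** First dose 11 March, true onset 20 March, onset day not recorded.
- True study day (SAP 10.3): 20 − 11 + 1 = 10.
- Imputed onset (SAP 10.1.1): 1 March, so the study day is 1 − 11 = −10.
- Status under SAP 10.3: before first dose, not treatment-emergent.

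**Share affected.** Inputs from the documents: the first-of-month rule (SAP 10.1.1), the *after first dose* definition (SAP 10.3) and the 21-day cycle (SAP 5.0). Assumptions not in the documents: first dose equally likely on each day of a four-year calendar (2018–2021, 1,461 days), and onset equally likely 0 to 20 days later. That gives 1,461 × 21 = 30,681 combinations.

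- Onset in the same calendar month as first dose: 20,601, and 20,601 / 30,681 = 67.1%. As a cross-check, the mean offset is 10 days and the mean month is 1,461 / 48 = 30.44 days, so 1 − 10 / 30.44 = 67.1%.
- Strict reading (*after*): all 20,601 lose treatment-emergent status. This is 100% of the day-missing events in the first-dose month and 67.1% of all day-missing events with onset in cycle 1.
- Lenient reading (*on or after*): only subjects first dosed on the 1st escape, which is 48 × 21 = 1,008 combinations. The remainder is 20,601 − 1,008 = 19,593. That is 95.1% of 20,601 and 63.9% of 30,681.

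The share falls as the onset window lengthens:

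| Onset window after first dose | Share of day-missing AEs affected (lenient to strict) |
|---|---|
| 21 days | 63.9% to 67.1% |
| 42 days | 35.1% to 37.5% |
| 84 days | 17.5% to 18.7% |

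**After the correction.** Onsets in the first-dose month are set to the first-dose date, and events on or after that date are counted. None of the 30,681 combinations is then misclassified. If SAP 10.3 kept the word *after*, an onset imputed to the dose date would still fail the definition, so both places must change.

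**The case against.** The case against giving this much weight is substantial, and much of it stands.

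- **The events are not lost from the report.** A reader might infer that they vanish. They do not: SAP 13.2 also requires a summary of all AEs, full listings, and separate listings of AEs leading to discontinuation and fatal AEs. SAP 13.3 adds listings and summaries of all serious events and deaths without a treatment-emergent restriction. However, the all-AE summary mixes in events from procurement onward and is not broken down by grade or relation.
- **Partial dates may be few.** Protocol 9.0 assesses toxicity on Day 1 of every 21-day cycle, and Protocol 14.5 requires serious events to be reported within 24 hours. The percentages above are shares of day-missing AEs, not of all AEs. Fully dated events are unaffected.
- **The effect on Vigil reactions is weaker.** Vigil is first given on Day 15. With Day 1 chemotherapy as first dose, onsets on Days 15–21 have a mean offset of 17 days, so 1 − 17 / 30.4 = 44% of day-missing ones are affected and more than half keep their status. The injection-site check planned for Day 16 also makes a missing onset day less likely.
- **SAP 13.2's definition is not purely date-based.** A worsening recorded with its own full date would still qualify. This does not rescue a new event with a missing day, because SAP 10.1.1 names treatment-emergent status as the use of the imputed date.
- **An early start could be called conservative because it lengthens duration.** That is not the use the SAP gives for it.

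A reader might also infer that a missing month sends every AE in the calendar year of first dose before treatment. SAP 10.1.1 refers only to similar logic and never states 1 January. A missing month is also an unlikely gap at three-weekly visits, so no percentage should be attached to it. Nor do the documents support a claim of bias between arms, since the rule is the same in both. The primary endpoint is untouched, because SAP 10.1.2 allows no imputation for it.

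**Conclusion.** The rule is wrong as written. SAP 10.1.1 and 10.3 together class every AE with a missing onset day in the first-dose month as pre-treatment, contrary to the section's own principle, and nothing in either document overrides this. The only exception is a subject first dosed on the 1st, and only if *after* is read as *on or after*. The consequence is removal from seven treatment-emergent summaries, not from the safety report. Under uniform first-dose dates and onsets, about 64–67% of day-missing AEs with onset in cycle 1 are affected. The number of such AEs is not given, so the absolute effect cannot be computed and may be small. The error runs in one direction, towards fewer treatment-emergent events, and is worth correcting before database lock because the correction is simple.

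**What to change.** 1. In SAP 10.1.1, give AEs their own rule. If the known parts of the onset date do not exclude onset on or after first dose, and the recorded end date is not before first dose, set onset to the first-dose date and flag the event as treatment-emergent. Keep the first-of-month rule for medications and medical history.
2. In SAP 10.3, change the treatment-emergent definition from *after* to *on or after* first dose.
3. In the same section, state one reference date: first administration of any study treatment. SAP 10.3 now refers variously to treatment drug, clinical trial material and study drug. In Group A, chemotherapy starts on Day 1 and Vigil on Day 15, so these terms could point to different days.

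The cost is short edits in two SAP sections and the matching change to the derivation. No new data are needed. The downside is that a few truly pre-dose events may be counted as treatment-emergent, which is the direction the SAP's stated principle calls for.

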10.1.2 Non-Date Values

Every effort will be made to obtain the protocol-required data for all study assessments that are scheduled for each scheduled visit for all subjects who have been enrolled. The primary endpoint is progression free survival, survival models (Kaplan-Meier estimates and Cox model) which take into account censored observations will be used. There will be no imputation for missing data for the primary endpoint.

10.2 Visit Windows

Study visit periods will be windowed as applicable as shown in Section 6.0.

Values will be presented for all scheduled study visits according to the nominal visit obtained from the CRF. If an unscheduled visit falls in a visit window with an existing nominal visit assessment, the nominal assessment will be used for summary presentation. If no nominal visit assessment exists for a visit window with unscheduled visit(s), then the latest unscheduled visit within the visit window will be used. If multiple nominal assessments are collected within the same visit, the latest value and corresponding date will be used for summary presentation.

All values will be included in the data listings.

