- 8. Serum chemistries (creatinine, glucose, total protein, blood urea nitrogen (BUN), total carbon dioxide (CO2), albumin, total bilirubin, alkaline phosphatase, and aspartate transaminase (AST) and/or alanine transaminase (ALT)) and electrolytes (total calcium, chloride, potassium, sodium) must be performed.
- 9. Blood collection for immune function analysis (ELISPOT).
- 10. Plasma collection for immune function analysis (ctDNA).
- 11. Pregnancy test for those of childbearing potential.
- 12. Submission to Gradalis, Inc. of preferably 20 unstained tumor slides or tissue block for correlative immunohistochemistry assay. These slides should correlate with tumor procured for vaccine manufacture.

Assessments During Treatment

The following evaluations will be performed on Day 1 of each cycle (1 Cycle = 21 days \pm 3 days) (unless otherwise specified):

- 1. *A physical examination, including vital signs and body weight.
- 2. *A toxicity assessment (CTCAE v 5).
- 3. *Assessment of concomitant medications.
- 4. Radiological assessment of disease status with CT chest /abd/pelvis (MRI abd/pelvis may be substituted for CT abd/pelvis) every 6 weeks ± 7 days from Cycle 1 regardless of treatment arm assignment or treatment delay. The methods used for prestudy assessments (e.g., CT or MRI) should be used throughout the study. If possible, the same equipment should be used each time.
- 5. *A CBC with differential and platelet count.
- 6. *Serum chemistries (creatinine, glucose, total protein, blood urea nitrogen (BUN), total carbon dioxide (CO2), albumin, total bilirubin, alkaline phosphatase, and aspartate transaminase (AST) and/or alanine transaminase (ALT)) and electrolytes (total calcium, chloride, potassium, sodium).
- 7. Blood collection for immune function analysis (ELISPOT) on Day 1 (prior to chemotherapy administration) at Cycles 2, 4, and 6.
- 8. Plasma collection for immune function analysis (ctDNA) on Day 1 prior to chemotherapy administration at Cycles 2, 3, 4 and 6.
- 9. *Assessment of Karnofsky Performance Status or LS.
- 10. Group A and B participants: oral temozolomide 100 mg/m² daily (Days 1 5, total dose 500 mg/m²/cycle)
- 11. Group A and B participants: oral irinotecan 50 mg/m² daily (Days 1 5, total dose 250mg/m²/cycle)
- 12. Group A participants: Vigil 1.0 x 10⁶ cells/injection, intradermally on Day 15.
- 13. Cross-over Subjects: Vigil 1.0 x 10⁶ cells/injection, intradermally every 21 days

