13.4 Laboratory Evaluations

Laboratory assessments and change from baseline will be summarized with descriptive statistics by panel, test, treatment group, and time point. Additionally, abnormal results will be summarized with frequencies and percentages by clinical significance, panel, test, treatment group, and time point.

A data listing will display all laboratory test results and findings.

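### The planned laboratory tables omit unscheduled mid-cycle results whenever a scheduled value exists, and no worst-grade laboratory table fills the gap

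*SAP*

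**What the plan says.** SAP 10.2 takes its windows from the schedule: "Study visit periods will be windowed as applicable as shown in Section 6.0". Three rules then choose the value to summarise:

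- Scheduled against unscheduled: "If an unscheduled visit falls in a visit window with an existing nominal visit assessment, the nominal assessment will be used for summary presentation".
- Scheduled value missing: "If no nominal visit assessment exists for a visit window with unscheduled visit(s), then the latest unscheduled visit within the visit window will be used".
- Several scheduled values: "If multiple nominal assessments are collected within the same visit, the latest value and corresponding date will be used for summary presentation".

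The section also says: "All values will be included in the data listings".

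SAP 13.4 summarises laboratory values and changes from baseline by visit, and adds that "abnormal results will be summarized with frequencies and percentages by clinical significance, panel, test, treatment group, and time point". Neither section names a table of worst post-baseline value, CTCAE laboratory grade, or shift from baseline.

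On timing, Protocol 9.0 (Assessments During Treatment) states: "The following evaluations will be performed on Day 1 of each cycle". The list that follows includes "A CBC with differential and platelet count" and serum chemistry, for both arms. The same section, and footnote 1 of the schedule in SAP 6.0, let subjects who are stable at the end of Cycle 4 move these evaluations to Day 15 if the sponsor approves.

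**The concern.** Bloods taken at the start of a cycle show counts after most of the previous cycle has passed. A low count found between visits, for example because the patient was unwell, is the result a safety reader most wants to see. The by-visit tables have no reliable place for it.

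Cytopenia matters here. Protocol 8.5 allows growth factor after Day 5 to help neutrophils recover. The Protocol Section 2 table that attributes events to Vigil, temozolomide and irinotecan lists Grade 3 and 4 falls in neutrophils and platelets. Protocol 14.3 counts cytopenias among the expected effects of Vigil, so their frequency by arm bears on the investigational product itself. SAP 8.2 lists laboratory assessments as a safety endpoint separate from adverse events.

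At stake is whether the measured laboratory comparison between arms can show transient toxicity, or whether that rests on adverse event reporting in an open-label trial.

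**Working it through.** The plan states no laboratory abnormality rate to reproduce, so this is a check of the rules against the schedule.

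**Inputs.** The cycle is 21 days with a ± 3 day tolerance (Protocol 9.0; SAP 6.0, footnote 1). Bloods are due on Day 1 by default. SAP 6.0 gives no start and end day for a laboratory window, so two readings are possible.

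**Reading 1: the window is Day 1 ± 3 days.**
- Days covered: 2 × 3 + 1 = 7, namely Days 19 to 21 of the preceding cycle and Days 1 to 4.
- Days not covered: 21 − 7 = 14, namely Days 5 to 18; 14/21 = 67%.
- A result from Days 5 to 18 has no row. The rule preferring the scheduled value never reaches it; it drops out because the table is by scheduled visit. It could not stand in for a missed Day 1 value either.
- An unscheduled result inside the 7 days loses to the Day 1 value if there is one.

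**Reading 2: the window is the whole cycle.**
- Every unscheduled result in the cycle competes with the Day 1 value and loses whenever that value exists.
- If Day 1 is missing, the latest unscheduled result enters, even if an earlier one was worse.

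**Common result.** On both readings, an unscheduled mid-cycle result is absent from the laboratory tables when the Day 1 value exists.

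**Tie-breaks.** Protocol 7.2 allows treatment to be delayed for up to three weeks for recovery from toxicity. If a site repeats a count under one visit label until it is acceptable, choosing the latest value selects the recovered one. This depends on how sites label repeats, which the documents do not say.

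**Day 15 draws.** From Cycle 5 some scheduled bloods may be taken on Day 15. Under Reading 1 that day lies outside the Day 1 window. SAP 10.2 otherwise follows the visit name on the case report form, so a later-cycle row could mix Day 1 and Day 15 draws. Group A attends on Day 15 for Vigil and Group B has no treatment that day, so uptake could differ by arm. That is an inference; the option itself is open to both arms.

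**Why no rate is given.** The shortfall depends on how often mid-cycle abnormalities occur, how many are sampled, and how many persist to the next scheduled draw. The documents give none of these.

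**The case against.** One value per visit is an ordinary rule for summaries over time, and it contradicts nothing in the protocol. That stands, and the rule should stay for that purpose.

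The strongest counter-argument is that toxicity is captured elsewhere. Protocol 14.1 counts an abnormal laboratory finding as a possible adverse event, Protocol 14.4 requires all adverse events to be recorded, and SAP 13.2 tabulates treatment-emergent events by CTCAE severity at each subject's maximum, outside the visit windows. The Protocol Section 2 table cited above is itself an adverse event table. So a reader might infer that Grade 3 and 4 cytopenia would go unreported; the documents do not support this. What remains is that neither document sets a threshold at which a laboratory value must be entered as an adverse event. Entry rests on the investigator's judgement, with treatment known, and no planned table derives grades from all the measured values.

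Three other stronger readings also fail:
- That all unscheduled results are discarded: they are summarised when they fall in a window with no scheduled value, and they are always listed.
- That bloods are only ever drawn on Day 1: Day 15 is possible after Cycle 4.
- That the comparison between arms is biased in a known direction: the rule applies to both arms, and nothing shows a differential effect.

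Two limits stand in full. An abnormality for which no blood was drawn is lost through the schedule, and no SAP change recovers it. A worst-value table also gives the more frequently sampled arm more chances to show a low value.

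**Conclusion.** The point holds for the laboratory tables only. As planned, they can understate transient mid-cycle abnormalities, because unscheduled results are left out when a scheduled value exists, ties go to the latest date, and no worst-grade or shift table is planned. On the Day 1 ± 3 day reading, 14 of every 21 days lie outside any window; on the whole-cycle reading, the Day 1 value prevails throughout. The conclusion needs neither reading to be the correct one, but it does assume that some unscheduled bloods are drawn mid-cycle.

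No percentage should be attached to the understatement, since any such figure would rest on inputs the documents do not contain. PFS, OS and ORR are not affected. This is a cheap improvement to safety reporting, not a flaw that threatens the trial's conclusions.

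**What to change.** In SAP 10.2, limit the one-value-per-visit rule to summaries over time, such as means and changes from baseline. State the first and last day of each laboratory window, and say how Day 15 draws after Cycle 4 are labelled and in which row they appear.

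In SAP 13.4, add two tables by arm that use all post-baseline values, scheduled and unscheduled: worst CTCAE grade per subject for each gradable test, and shift from baseline to worst grade. Cut Group B at cross-over to Vigil (Protocol 10.0), so that later results are not counted against chemotherapy alone. Report the number of samples per patient by arm beside them.

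The cost is a few SAP sentences and two standard tables from data already collected and listed; no visit, blood draw or treatment rule changes. There are two downsides. Reported laboratory toxicity will look less favourable than in the by-visit tables. Unequal sampling between arms can also affect a worst-value comparison; the sample counts let a reader judge that but do not remove it.
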